## 2.4 RATIONALE

BRCA proteins and other DNA repair mechanisms, including base excision repair and direct reversal of DNA damage, function in a complementary manner to remove hurdles that impede DNA cell division. Therefore, in BRCA cells, inhibition of complementary repair function should increase the sensitivity of cancer cells to killing by both endogenous mutagens and exogenous agents. The PARP inhibitor ABT-888, validated in our pre-clinical work, will be tested alone and in combination with carboplatinum this clinical trial.

**Rationale for selection of starting doses:** For ABT-888, the chosen starting dose is based on an ongoing phase 1 continuous dosing study (NCI#8282), in which only one of six patients at the level of 50mg BID had a DLT. Carboplatinum was able to be delivered at AUC 6 in the phase I combination study of carboplatinum, paclitaxel and ABT-888 (NCI#7967). While paclitaxel will not be used in this study, ABT-888 may behave synergistically with carboplatin and result in added toxicity, primarily myelosuppression, consequently a dose modification scheme for carboplatin is included. Although we expect both arms of this regimen to be well tolerated, we have established guidelines and criteria which will be used to flag an unexpected number of patients who experience unacceptable toxicity. These rules will be applied to both arms independently, although the main motivation for such detailed monitoring is based on the combination arm.

The MTD for carboplatin dosing is established as AUC 5. The previous dose escalation schedule labelled as Table 3a has now been deleted. An expanded safety lead-in attempted to maximize the ABT-888 exposure (Table 3) while keeping the carboplatin at AUC 5. This is prompted by observation of grades 3 & 4 thrombocytopenia with an otherwise well-tolerated regimen in the initial safety lead-in experience with the first 9 patients. Given that the Phase I continuous dosing study of ABT-888 (NCI#8282) passed 400mg BID, it seems likely that ABT-888 in combination with carboplatin can be escalated safely to at least 200 mg BID in the expansion phase. [Note: safety lead-in was completed with 25 patients, and the MTD was established with carboplatin AUC 5, ABT-888 150 mg BID]

### 3 PATIENT SELECTION

#### Study Population:

The infrastructure of the multi-institutional California Cancer Consortium with Pennsylvania (CCCP) will be used to obtain access to the specific CTEP agent, and facilitate development, conduct and dissemination of the proposed targeted therapy protocol, which will be supported under a N01 phase II contract (N01CM57018). Along with the 5 affiliated CCCP institutions (City of Hope, University of California at Davis, University of Southern California, University of Pittsburgh, and Pennsylvania State University), five other N01-supported consortia are committed to participating in the clinical trial, including this latest amended version (New York Consortium [even though this consortium is no longer part of the N01 contract mechanism, the participating institutions have agreed, and demonstrated ongoing commitment to accruing patients]; University of Chicago Consortium; Mayo Clinic Phase 2 Consortium, Princess Margaret Hospital, Toronto, Canada; MD Anderson Cancer Center, Houston; letters of collaboration are in the Appendix). All patient registrations will be handled centrally via the CCCP coordinating center.

Clinical cancer genetics resources will be used for enhanced recruitment, with strong minority representation, including our established hereditary cancer registry, community-based *Cancer Screening & Prevention Program Network* (CSPPN) and liaisons with advocates/organizations for national recruitment and dissemination. Data mining from the existing COH CSPPN cohort (described in Preliminary Results) identified approximately 65 *BRCA* carriers with locally advanced (stage III) or metastatic BC, and we accrue approximately 110 new *BRCA* carriers with BC in the CSPPN annually. CCCP partner institutions each have a set of known *BRCA* carriers with BC, and most have a formal cancer genetics unit. For example, USC has accrued 49 *BRCA* carriers with BC, and University of Pittsburgh estimates approximately 20 new *BRCA*-associated BC cases each year. Summation of estimates from the other collaborating consortia indicate approximately 90 potentially eligible women with advanced *BRCA*-associated BC will be identified annually. Overall, after selecting for advanced stage cases, we estimate that 5 of 22 potentially eligible cases across the consortia will be accrued to the study every month over the projected 18-month accrual period. Additional procedures to augment accrual include listing on COH Clinical Trials On-line, posting the studies on the FORCE web site (per Advocate [name]; letter in Appendix), and a newsletter style announcement distributed (email and USPS) to a mailing list of regional/referring physicians. The Clinical Cancer Genetics team (PI: [name]) will hold monthly teleconferences with the genetics units across the consortia to review progress identifying *BRCA* carriers as candidates for study, and disseminate any updated promotional materials.

Treating physicians who are approved by their respective Institutional Review Boards (IRB) will be responsible for explaining the study, answering questions and obtaining informed consent, according to regulatory guidelines and to respective IRB guidelines.

Ongoing understanding will be assessed and questions will continue to be answered by the treating physicians.

### **3.1 ELIGIBILITY CRITERIA**

- 3.1.1 Patients must be female, and must have histologically confirmed breast cancer that is metastatic or locally advanced, unresectable and for which standard curative measures do not exist or are no longer effective.
- 3.1.2 Patients must have a known deleterious *BRCA* mutation confirmed by report from a CLIA certified laboratory (generally Myriad Genetics Laboratory). It is expected that *BRCA* testing will be covered as medically necessary care by the patient's insurance carrier.
- 3.1.3 Measurable disease by RECIST criteria. (Evaluable disease is allowed only for the Safety Lead-In phase).
- 3.1.4 Prior chemotherapy regimens for metastatic disease are completed, at least 3 weeks prior to starting therapy. Prior radiation and hormonal treatment must be completed at least 1 week prior to starting therapy.
- 3.1.5 Female, age  $\geq 18$  years. Because no dosing or adverse event data are currently available on the use of ABT-888 in patients  $<18$  years of age, children are excluded from this study.
- 3.1.6 ECOG Performance Status 0-2 (See Appendix A).
- 3.1.7 Life expectancy of greater than four months.
- 3.1.8 Patients must have normal organ and marrow function as defined below

- absolute neutrophil count	$\geq 1,500/\text{mcL}$
- platelets	$\geq 100,000/\text{mcL}$
- total bilirubin	$\leq 1.5 \times$ institutional upper limit of normal
- AST(SGOT)/ALT(SGPT)	$\leq 2.5 \times$ institutional upper limit of normal unless there is evidence of liver metastasis, in which case the AST(SGOT)/ALT(SGPT) must be $\leq 5 \times$ institutional upper limit of normal within normal institutional limits
- creatinine	

OR

- creatinine clearance	$\geq 60 \text{ mL/min}/1.73 \text{ m}^2$ for patients with creatinine levels above institutional normal.
------------------------	-----------------------------------------------------------------------------------------------------------

- 3.1.9 If a woman is of child-bearing potential, a negative serum or urine pregnancy test is required. (The effects of ABT-888 [NCI 737664] on the developing human fetus are unknown. For this reason and because PARP Inhibitor agents are known to be teratogenic [see Investigator Brochure], women of child-bearing potential and men must agree to use adequate contraception (hormonal or barrier method of birth control;

abstinence) prior to study entry and for the duration of study participation. Participants should agree to use contraception for at least 3 months after the completion of study therapy. Should a woman become pregnant or suspect she is pregnant while participating in this study, she should inform her treating physician immediately.)

- 3.1.10 Ability to understand and the willingness to sign a written informed consent document.

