**Patients will discontinue treatment by December 31, 2024, or earlier.**

**Stratum 1: BRCA1-associated Breast Cancer: ABT-888 alone, 400 mg PO BID, daily x 21 days. Initially 10 patients will be treated. If 0 or 1 responses are seen (CR or PR) this stratum will close. If there are two or more responses, an additional 12 patients will be accrued for a total of 22 patients on this stratum.**

**Stratum 2: BRCA2-associated Breast Cancer: ABT-888 alone, 400 mg PO BID, daily x 21 days. Initially 10 patients will be treated. If 0 or 1 responses are seen (CR or PR) this stratum will close. If there are two or more responses, an additional 12 patients will be accrued to a total of 22 patients on this stratum.**

**Patients progressing on the Phase II component will be required to have a 1-week interval of no treatment prior to being treated with the combination (as established during the safety lead-in), and be required to meet the pre-treatment eligibility requirements (other than the prior therapy requirements). Following progression, if patients meet the eligibility requirements, the patients will initiate treatment with carboplatin AUC 5 plus ABT-888 150 mg BID (as the Maximum Tolerated Dose of the combination established during the safety lead-in).**

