## 6 DOSING DELAYS/DOSE MODIFICATIONS

Patients should meet the laboratory parameters outlined in section 3.1.8 and the performance status in section 3.1.6 before initiation of each cycle of therapy. All toxicities (except alopecia and lymphopenia, hyperglycemia, hypoalbuminemia, elevated serum alkaline phosphatase, WBC, and hemoglobin) should have resolved to grade 1 or lesser severity before initiation of the next cycle of therapy.

Qualifying laboratory tests can be obtained up to 72 hours before planned initiation of therapy from the third cycle onwards.

Dose adjustments are to be made according to the organ system showing the greatest degree of toxicity. The descriptions and grading scales found in the revised NCI Common Terminology Criteria for Adverse Events (CTCAE) version 5.0 will be utilized for AE reporting beginning April 1, 2018. All appropriate treatment areas should have access to a copy of the CTCAE version 5.0. A copy of the CTCAE version 5.0 can be downloaded from the CTEP web site [http://ctep.cancer.gov/protocolDevelopment/electronic\\_applications/ctc.htm](http://ctep.cancer.gov/protocolDevelopment/electronic_applications/ctc.htm).

The dose levels and the general approach to dose modification of ABT-888 therapy is shown in Table 4. Specific dose modification information for some AEs are provided in other sections. AEs should be treated with the appropriate maximum supportive care, and dose reductions should be clearly documented in the electronic case report form (eCRF).

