**Table 6: Management of anemia**

CTCAE Grade	Definition	ABT-888 Dose
2	Hb <10 but $\geq 8$ g/dL	Give appropriate supportive treatment and

CTCAE Grade	Definition	ABT-888 Dose
		investigate causality. Investigator judgement to continue ABT-888 or interrupt dose for a maximum of 3 weeks. If repeat Hb <10 but $\geq 8$ g/dL, dose interrupt until Hb $\geq 10$ g/dL for maximum of 3 weeks and upon recovery dose reduce by 50 mg BID from the current dose level as a first step and by another 50 mg BID as a second step.
3	Hb <8 g/dL	Give appropriate supportive treatment and investigate causality. Interrupt ABT-888 until improved to Hb $\geq 10$ g/dL. Upon recovery dose reduce ABT-888 by 50 mg BID.
BID = twice daily; Hb = hemoglobin		

Common treatable causes of anemia (e.g., iron, vitamin B12 or folate deficiencies and hypothyroidism) should be investigated and appropriately managed. In some cases management of anemia may require blood transfusions. Any subsequently required dose interruptions related to development of anemia, or coexistent with newly developed neutropenia, and/or thrombocytopenia, reduce ABT-888 dose to no more than two dose reductions.

If Hb drops to <8 g/dL despite the dose reduction or more than one blood transfusion is required to recover Hb levels with no alternative explanation for the anemia, ABT-888 should be permanently discontinued.

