### **Management of prolonged hematological toxicities while on study treatment**

If a patient develops prolonged hematological toxicity such as:

- $\geq 2$  week interruption/delay in velaparib due to CTCAE Grade  $\geq 3$  anemia (Hb <8 g/dL) and/or development of blood transfusion dependence
- $\geq 2$  week interruption/delay in ABT-888 due to CTCAE Grade  $\geq 3$  neutropenia (ANC <1  $\times 10^9/L$ )

- $\geq 2$  week interruption/delay in ABT-888 due to CTCAE Grade  $\geq 3$  thrombocytopenia and/or development of platelet transfusion dependence (Platelets  $< 50 \times 10^9/L$ )

Check weekly differential blood counts including reticulocytes and peripheral blood smear. If any blood parameters remain clinically abnormal after 3 weeks of dose interruption, the patient should be referred to a hematological oncologist for further investigations. Bone marrow for evaluation and cytogenetics should be considered at this stage according to standard hematological oncology practice. ABT-888 should be discontinued if blood counts do not recover to CTCAE Grade  $\leq 1$  within 3 weeks of dose interruption.

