## 14 STATISTICAL CONSIDERATIONS

### 14.1 STUDY DESIGN/ENDPOINTS

The design of this Phase II trial is also described in Section 5.0.

All patients who begin treatment as part of this trial will be accounted for in the summary of results, and the outcome status (in terms of toxicity, response, reason off study, progression, and survival) will be reported.

The toxicities observed will be summarized in terms of type (organ affected or laboratory determination such as absolute neutrophil count), severity (by CTCAE and nadir or maximum values for the laboratory measures), time of onset (i.e. course number), duration, and reversibility or outcome. Tables will be created to summarize these toxicities and side effects by course.

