#### **Toxicity/Safety Monitoring:**

Although we expect this regimen to be well tolerated, we have established guidelines and criteria which will be used to flag an unexpected number of patients who experience unacceptable toxicity (TOX). These rules will be applied to both the single ABT-888 treatment and the combination treatment independently, although the main motivation for such detailed monitoring is based on the combination arm. Stratum will be analyzed separately.

Unacceptable toxicity (TOX) will be defined as any toxicity that results in a  $> 2$  week delay in treatment or any toxicity resulting that the patient be taken off treatment. Patients who do not complete the first 2 cycles of treatment with the prescribed dose and do not experience a TOX will NOT be used in the decision to consider halting the trial because of toxicity and will be considered invaluable for TOX.

Criteria for flagging an excessive number of patients with TOX are based on the sequential probability ratio test with  $\alpha=0.10$ ,  $\beta=0.10$ ,  $p_0=0.05$  and  $p_a=0.25$ . Every time a

patient is classified as having had a TOX, the cumulative number of patients (X) who have experienced a TOX will be compared to the number of patients (N) who are evaluable for toxicity. If the number of patients, N, is greater than Nx, the number given in the bottom row of the Table below, then accrual will not be suspended. If N is less than or equal to Nx, then accrual will be suspended for review of the data. The Nx values do not correspond to the interim analysis accrual goal, as these rules are examined when a patient experiences a TOX regardless of accrual, and we expect fewer patients evaluable for TOX than response (all treated patients).

Table: Criteria for Suspending Accrual to Evaluate Toxicity			
X: # pts who experienced a TOX	2	3	4
N x : Suspend trial of # evaluable pts. (N) is ≤ N x	≤6	≤14	≤21

These rules were selected to ensure a low probability that the trial would be suspended if the true chance of unacceptable toxicity were less than 5% and a high probability that the trial would be suspended if the true chance of unacceptable toxicity were 20-25%. The Table below summarizes these probabilities. The values in the table below are based on 10,000 simulations and are accurate to ±0.01 (based on a 95% confidence interval).

Table: Probability of Suspending Accrual Because Too Many Patients Experienced a TOX						

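### Section 14.1 tabulates toxicity without reference to the pre-study value, so anemia and other abnormality already present at entry is reported as on-treatment toxicity and, on one reading of Table 6, can count as TOX

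*Combined protocol and SAP*

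**What the plan says.** **Entry.** Section 3.1.8 states "Patients must have normal organ and marrow function as defined below" and then limits ANC, platelets, bilirubin, AST/ALT and creatinine or creatinine clearance. Hemoglobin appears in neither 3.1 nor 3.2. On earlier treatment, 3.1.4 says "Prior chemotherapy regimens for metastatic disease are completed, at least 3 weeks prior to starting therapy"; it does not ask that the toxicity of that chemotherapy has resolved. Before the post-progression combination, section 5.1 has patients "be required to meet the pre-treatment eligibility requirements (other than the prior therapy requirements", so the same list, again without hemoglobin, is applied a second time.

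**On treatment.** Section 6 says that toxicities "should have resolved to grade 1 or lesser severity before initiation of the next cycle of therapy", but it puts hemoglobin on the list of exceptions. Table 6 works in absolute bands (Hb below 10 and at least 8 g/dL; Hb below 8 g/dL). For the lower band it says "Interrupt ABT-888 until improved to Hb" of at least 10 g/dL, and it sets the same recovery target when a value in the upper band is repeated. The part of 6.1 on prolonged hematological toxicity says "ABT-888 should be discontinued if blood counts do not recover to CTCAE Grade" 1 or lower within 3 weeks of interruption. None of these rules mentions the entry value.

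**Analysis.** Section 14.1 summarises toxicity by type, by "severity (by CTCAE and nadir or maximum values for the laboratory measures", and by course of onset. Under 14.3, "Unacceptable toxicity (TOX) will be defined as any toxicity that results in a" delay of more than 2 weeks, or that takes the patient off treatment. Neither text refers to the pre-study value or to attribution.

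**The concern.** A secondary objective in 1.2 is to describe the safety of ABT-888 alone and with carboplatin. There is no control arm, so the toxicity tables are read as the effect of treatment. A patient who enters with low hemoglobin and never changes still contributes an anemia grade and a nadir to those tables, which biases them upward. The same holds for a symptom left over from earlier chemotherapy.

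The combination phase adds a second route. The part of 6.1 on anemia calls it a common reaction to ABT-888, and patients start the combination after only one week off drug. The TOX rule is applied to single-agent and combination treatment independently, so anemia carried over from the first phase can be charged to the second. Section 14.3 names the combination as the main reason for this monitoring.

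**Working it through.** **1. Which abnormalities can pass through entry.** ANC of at least 1,500/mcL and platelets of at least 100,000/mcL at entry lie above the grade 3-4 action range of Table 5 (ANC below 1.0 G/L, platelets below 50 G/L). Liver and renal values are also bounded. The open items are hemoglobin and non-laboratory toxicity.

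**2. A patient with Hb 9 g/dL at entry and at every later count.**
- Entry: eligible, since 3.1.8 is silent on hemoglobin.
- First on-treatment count: upper band of Table 6. Continuing or interrupting is left to the investigator, with causality to be looked into.
- Next count: if *repeat* means a further value in the band, the drug is held until Hb reaches 10, for at most 3 weeks. Hb stays at 9, the hold passes 2 weeks, and the TOX definition is met with no change from entry. If *repeat* means a recurrence after recovery, which is how Table 5 can be read, this step is not triggered.
- Next cycle: section 6 exempts hemoglobin from recovery, while Table 6 requires it. The two do not agree.
- 14.1: on either reading, she is tabulated with anemia at her entry grade and a nadir of 9.

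**3. Reproducing the plan's monitoring rule.** Inputs from 14.3: α = 0.10, β = 0.10, p0 = 0.05, pa = 0.25. The upper limit of the sequential probability ratio test is

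N_X = X + [X·ln(pa/p0) − ln((1−β)/α)] / ln((1−p0)/(1−pa)),

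with ln 5 = 1.609, ln 9 = 2.197 and ln(0.95/0.75) = 0.2364. X = 2, 3, 4 gives 6.32, 14.13 and 21.94, so 6, 14 and 21, as printed.

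The suspension probability was computed exactly. Let f_n(x) be the probability of x TOX after n patients without suspension. Then f_n(x) = (1−p)·f_{n−1}(x) + p·f_{n−1}(x−1), and any path that reaches 2 by N = 6, 3 by N = 14 or 4 by N = 21 is moved to suspended.

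| True TOX rate | Plan, N = 21 | Exact |
|---|---|---|
| 5% | 0.06 | 0.056 |
| 10% | 0.25 | 0.243 |
| 15% | 0.49 | 0.489 |
| 20% | 0.72 | 0.706 |
| 25% | 0.85 | 0.854 |

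The 20% entry differs by 0.014, slightly more than the plan's stated simulation accuracy of 0.01. That is immaterial here.

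**4. Effect of counting unchanged entry abnormality.** Let q be the share of patients who meet TOX only because an unchanged entry abnormality leads to a hold of more than 2 weeks or to removal. The documents give no value, so q is an assumption, taken as independent of drug-caused TOX. With a drug-caused rate of 5%, the counted rate is 1 − 0.95·(1 − q).

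| q (assumed) | Counted rate | P(suspend), per stratum |
|---|---|---|
| 0 | 0.0500 | 0.056 |
| 1% | 1 − 0.95 × 0.99 = 0.0595 | 0.083 |
| 2.5% | 1 − 0.95 × 0.975 = 0.0738 | 0.131 |
| 5% | 1 − 0.95 × 0.95 = 0.0975 | 0.231 |

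Note that q is narrower than the share of patients with an abnormal entry value, because the abnormality must also lead to the delay or removal.

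**The case against.** **Attribution is handled elsewhere.** Section 6 lets the investigator hold or modify drug when a toxicity is attributed to it, Table 6 asks for causality to be investigated, and 7.2 grades attribution down to unrelated. This stands for management and makes the route to TOX less likely. It does not reach the tables in 14.1 or the wording of TOX, neither of which has an attribution condition.

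**The Hb 9 patient would be discontinued.** A reader might infer this, and with it a loss from the response assessment with no drug effect. The documents do not clearly support it. The anemia item in the prolonged-toxicity part of 6.1 is Hb below 8 g/dL or transfusion dependence. Table 6's permanent stop needs Hb below 8 despite dose reduction, or more than one transfusion, without another explanation. Elsewhere 6.1 calls for hematology referral after 3 weeks without recovery. What can be shown is a possible hold of more than 2 weeks.

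**Entry symptoms go unrecorded.** The adverse event row of the calendar has no pre-study mark, which invites this inference. But history, physical exam, performance status, CBC and chemistry are all done pre-study. The entry state is on record; it is simply not used as the reference.

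**TOX should count only worsening.** This is tempting, but a fall from Hb 9.9 to 8.0 stays within one Table 6 band. A drug-caused hold in that patient would drop out of a safety boundary. Keeping the broad definition is the cautious choice.

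**The harm is past.** The note to Table 4 says that the study was closed to accrual by 8/6/18 with 3 patients remaining, and suspension was in any case only for review of the data. The documents also do not show whether the present Table 6 applied during accrual. All of this stands, and it limits the point to reporting.

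**Absolute grade and nadir are a legitimate summary.** They are, and they should stay. Alone, in a single-arm trial, they cannot separate entry state from treatment effect.

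**Conclusion.** The point holds as a reporting weakness. Abnormality present at entry, mainly anemia and residual non-laboratory toxicity, enters the 14.1 tables as on-treatment toxicity and biases them upward. An unchanged Hb of 8 to below 10 g/dL can count as TOX if Table 6's repeat row is read as any further value in the band.

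The size of the bias cannot be derived from the documents. Under assumed shares of 1% to 5%, the false-suspension probability per stratum would be 0.083 to 0.231 rather than 0.056. With accrual closed, those figures show only how sensitive the TOX count is. What remains live is the interpretation of the toxicity tables and TOX counts. The primary response-rate design is not affected. Whether CTCAE grading itself refers to baseline was not assessed, because the CTCAE is not among the documents.

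**What to change.** **In 14.1**, add that laboratory toxicity is presented as pre-study grade against worst on-treatment grade, and that events worse than the pre-study grade are reported beside the absolute grades. For the combination phase, use a fresh value taken before its first dose as the reference. For symptoms, take the entry grade from the pre-study history and exam where these allow it.

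**In 14.3**, leave the TOX definition as it is. Whenever TOX counts are reviewed or reported, list each TOX patient's pre-study grade for the event concerned.

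**Reconcile** 3.1.8, the next-cycle rule in section 6, Table 6, the prolonged-toxicity part of 6.1 and the TOX definition for patients whose entry value already lies in an action range. In particular, section 6 exempts hemoglobin from recovery while Table 6 requires it, and the meaning of a repeat value needs stating. No clinical threshold is proposed here.

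**Cost:** a few sentences and one shift table per phase, from CBC, chemistry, history and exam already collected. There is no new visit or test. Grading entry symptoms from existing records takes some abstraction and will be less certain than the laboratory grades.
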